## 15.1.2 Adverse Events Leading to Study Treatment Discontinuation

The following overall frequency table will be prepared:

- TEAEs causing temporary discontinuation of study treatment
- TEAEs causing permanent discontinuation of study treatment
- Any TEAE leading to dose reduction of study treatment.

For the above categories the total number and rate (per patient-year of time on study) of TEAEs will be also reported.

## 15.2 Deaths, Other Serious Adverse Events, and Other Significant Adverse Events

#### **15.2.1 Deaths**

The following summaries for the deaths will be reported in a table:

- Number and percentage of Deaths
- Number and percentage for each Reason of Death (percentage calculated using the number of deaths as denominator).

The total number of deaths and rate (per patient-year of time on study) of deaths will be also reported.

A listing with the following columns will be presented:

- Patient ID
- Age (years)/ Sex/ Race/ Weight (kg)
- Date of first / last administration
- Last dose (unit)
- Number of doses

- Date of death
- Cause of death
- AE
- PT term.

## **15.2.2** Serious Adverse Events

A listing with the following columns will be presented:

- Patient ID
- AE
- PT term
- Start/ End Date of AE
- Duration of AE (days)
- Seriousness criteria (Results in death, Is life-threatening, Requires/Prolongs Hospitalization, Persistent/Significant Disability/Incapacity, Is a Congenital Anomaly/Birth Defect, Other)
- Relationship with study treatment (Related, Unrelated)
- Severity (Severe, Moderate, Mild)
- Action(s) taken with study treatment
- Outcome of Event (Fatal, Not recovered/not resolved, Recovered/resolved with sequelae, Recovered/resolved, Unknown)
- Relative Day from First Administration.

## **15.3** Clinical Laboratory Evaluation

Hematology assessment will be based on white blood cell count, hemoglobin, hematocrit, platelet count, ALC. For continuous variables, values and change from baseline values will be considered. The above variables will be evaluated descriptively by time point.

Any available results from JCV tests done will be summarized as status positive or negative. It will be summarized descriptively at baseline and for all the tests available during the study a listing with

- Patient ID
- Date of JCV test
- JCV test done? (Done/Not Done)
- Result (Positive or Negative)

will be reported.

Any available results for immunoglobulin will be summarized as continuous variable, with values and change from baseline values by timepoint.

Laboratory values that are outside the normal range will also be flagged in the data listings, along with corresponding normal ranges. The data listing will include the following columns:

- Patient ID
- Parameter (International System of Units (SI unit))
- Visit/Week
- Date of Collection (Relative Day)
- Value
- Change from Baseline
- Lower Range/Upper Range
- Normal Range Indicator (Low, High).

Boxplots of the laboratory values and boxplots of the change from baseline values will be reported by time point.

ALC will also be displayed as a line graph with the median cell counts on the y-axis (with bars for 1st and 3rd quartile extending above and below) and time points on the x-axis.

An additional summary of ALC by lymphopenia grade will be presented with proportion of patients in each category at each time point:

- Elevated: >4.8 x 109 cells/L
- Normal: 1.0 to 4.8 x 109 cells/L
- Grade 1 Lymphopenia: 0.8 to <1.0 x 109 cells/L
- Grade 2 Lymphopenia: 0.5 to <0.8 x 109 cells/L
- Grade 3 Lymphopenia: 0.2 to <0.5 x 109 cells/L
- Grade 4 Lymphopenia: <0.2 x 109 cells/L

These categories are consistent with the Common Terminology Criteria for Adverse Event (CTCAE) for lymphopenia AE grading (US Department of Health and Human Services. CTCAE version 4.0. 2009;4(03)).

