7.4 Cladribine Tablets

Cladribine (2-chloro-2'-deoxyadenosine [2-CdA]) is a synthetic anti-neoplastic drug that belongs to the subgroup of agents called purine analogs. In 2019, cladribine tablets were indicated for the treatment of patients with RMS, including relapsing-remitting multiple sclerosis (RRMS) and active secondary progressive multiple sclerosis (aSPMS), by the US FDA.

Three clinical trials for cladribine tablets have been completed (CLARITY, ORACLE MS and ONWARD), and data from these trials (Leist 2014; Montalban 2016; Giovannoni 2010), as well as the extension phase of the CLARITY trial (Giovannoni 2013) and the interim long-term follow-up data from a prospective registry (the PREMIERE registry), have provided information on the efficacy and safety of cladribine tablets. In total, the follow-up consisted of >10,000 person-years of exposure for both cladribine tablets and placebo, with over 8 years of follow-up for some patients.

In the CLARITY trial, patients with active RMS were randomized to placebo or cladribine tablets (3.5 or 5.25 mg/kg body weight) for 2 years; each dose showed significant benefits in rate of relapse, disability progression, and MRI measures (Giovannoni 2010). Treatment with cladribine tablets in CLARITY produced efficacy improvements that were maintained in patients treated with placebo in the extension phase (Giovannoni 2013).

Approximately 20% to 25% of the patients treated with 3.5 mg/kg as monotherapy developed transient Grade \geq 3 lymphopenia. Grade 4 lymphopenia was observed in 0.7% of patients. Overall, nearly 90% of patients recovered by the end of the trials. The remaining patients recovered during long-term follow-up without developing severe or opportunistic infections.

Herpes zoster infection is considered as an important identified risk of treatment with cladribine tablets. The observed incidence rates in the monotherapy oral cohort for herpes zoster infection were 0.86 adjusted adverse events (AEs) per 100 person-years for cladribine tablets 3.5 mg/kg vs. 0.20 for placebo, and for severe herpes zoster infection 0.9 vs. 0.5, respectively. The incidence of herpes zoster infection was higher during periods of Grade 3 or 4 lymphopenia compared to the time when the patients were not experiencing Grade 3 or 4 lymphopenia.

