Investigators are expected to assess patients' absolute lymphocyte count (ALC) in accordance with the USPI and to follow any other recommended monitoring and guidance as specified in the USPI. Based on this, investigators are expected to assess the ALC before initiating cladribine tablets in Year 1, before initiating cladribine tablets in Year 2, as well as 2 and 6 months after start of treatment in each treatment year or as clinically indicated. It is

. These data will be collected as

assumed that investigators will not exclusively assess the ALC, but rather the complete blood count (CBC) and, at some of these time points, also lymphocyte subsets and certain CC

available.

[figure not shown]
Patients with lymphopenia resulting in delay of the scheduled Year 2 treatment course are expected to receive the second treatment course once the lymphocyte count is appropriate (\geq 800 cells per microliter) consistent with USPI labelling and will be followed up until the end of the observation period. If the ALC drops to <500 cells per microliter, the patient should be actively monitored until values increase as per USPI. If the ALC drops to <200 cells per microliter, anti-herpes prophylaxis should be administered, and the patient should be monitored for infections. Such unscheduled additional hematology assessments as per clinical requirements should be documented as well.

An overview of the study design is shown in Figure 1.

Visits and assessments are detailed in the Schedule of Assessments (see Section 9.2.4).

Company substance code: Protocol number:

Figure 1. Study Design Schematic

^a Duration between stopping previous injectable DMD and start of cladribine tablets is at the discretion of the investigator.

^b Year 2 course may be delayed for some patients, according to the ALC. If Year 2 treatment is delayed, follow-up may continue through Month 30.

Note. Refer to Table 1 for more data collection details and assessments at each visit.

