¹ Life threatening in this context refers to a reaction in which the patient was at risk of death at the time of the reaction; it does not refer to a reaction that hypothetically might have caused death if more severe.

 2 Medical and scientific judgment should be exercised in deciding whether other situations should be considered as serious reactions, such as important medical events that might not be immediately life threatening or result in death or hospitalization but might jeopardize the patient or might require an intervention to prevent one of the other outcomes listed above. Such important medical events should be considered as serious.

Examples of such events are intensive treatment in an emergency room or at home for allergic bronchospasm, blood dyscrasias or convulsions that do not result in hospitalization or development of dependency or abuse. As a guidance, the important medical event terms list is intended to be used for assessment of suspected ADRs (see EMA/207865/2017).

Any suspected transmission via a medicinal product of an infectious agent is also considered a serious ADR.

Adverse Events of Special Interest

An adverse events of special interest (AESI) is an AE of scientific and medical concern specific to the Sponsor's product or program, for which ongoing monitoring and rapid communication by the investigator to the Sponsor can be appropriate. AESIs for monitoring should then be collected following the procedure for an SAE described in Section 11.4. The following events will be considered AESIs:

- Severe lymphopenia: defined as Grade 3 (<500 to 200 cells per microliter) or Grade 4 (<200 cells per microliter)
- Severe infection
- Tuberculosis
- Herpes zoster infection
- Progressive multifocal leukoencephalopathy
- Other opportunistic infection
- Malignancy

Events that Do Not Meet the Definition of a Serious Adverse Event

Elective hospitalizations (e.g. an overnight stay to facilitate therapy) are not considered as SAEs. However, all events leading to unplanned hospitalizations or unplanned prolongation of an elective hospitalization (e.g., undesirable effects of any administered treatment) must be documented and reported as SAEs.

Events Not to Be Considered an Adverse Event

Medical conditions present and documented at study start, that do not worsen in severity or frequency during the study are defined as baseline Medical Conditions and elective procedures and are NOT to be considered AEs.

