11.2 Severity of Adverse Events

Investigators should assess the severity/intensity of any AE as follows:

- Mild: The patient is aware of the event or symptom, but the event or symptom is easily tolerated.
- **Moderate:** The patient experiences sufficient discomfort to interfere with or reduce his or her usual level of activity.
- Severe: Significant impairment of functioning: the patient is unable to carry out usual activities.

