Abnormal Laboratory Findings and Other Abnormal Investigational Findings

No scheduled laboratory assessments are required by protocol. Nevertheless, laboratory data of medical importance, as deemed necessary and requested by the investigator as part of the patient's standard medical care, will be, when available, recorded into the eCRF by the investigator.

Abnormal laboratory findings and other abnormal investigational findings (e.g. on an electrocardiogram trace) should not be reported as AEs unless they are associated with clinical signs and symptoms or are considered otherwise medically important by the investigator or general practitioner. If an abnormality fulfills these criteria, the identified medical condition (e.g. anemia, increased alanine transaminase [ALT]) must be reported as the AE rather than the abnormal value itself.

Vital Signs, Physical Examinations, and Other Assessments

Weight will be collected at baseline when available.

Physical examination data will be collected during the course of routine clinical care. Abnormal physical examination findings should not be reported as AEs unless they are considered medically important by the investigator. If an abnormality fulfills these criteria, the identified medical condition must be reported as the AE rather than the abnormal physical examination finding itself.

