To collect all serious adverse events (SAEs), adverse drug reactions (ADRs), adverse events of special interest (AESIs) and special situations during treatment with cladribine tablets over a 24-month period	SAEs, ADRs, AESIs	Adverse event (AE) collected from signed Informed Consent Form (ICF); Treatment- Emergent Adverse Events (TEAEs) considered after first treatment administration through the 24- month treatment period (or 30 months if Year 2 treatment is delayed)	Section 15
CCI			

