### 15.1.1 All Adverse Events

If an AE is reported for a given patient more than once during the study, the worst severity and the worst relationship to study drug will be tabulated.

The following overall frequency table will be prepared:

- Any TEAEs
- Treatment related TEAEs (ADRs)
- Any serious TEAEs
- Treatment related serious TEAEs
- Any TEAE by severity (Severe, Moderate, Mild)
- Treatment related TEAE by severity (Severe, Moderate, Mild)
- TEAEs leading to death
- Treatment related TEAEs leading to death.

The total number of TEAEs and rate (per patient-year of time on study) of TEAEs will be also reported.

A table showing the TEAE by Primary SOC and PT will be reported.

A listing with the following columns will be presented:

- Patient ID
- AE

- PT term
- Start/ End Date of AE
- Duration of AE (days)
- Relationship to Cladribine
- Action on Cladribine
- Outcome
- Relative Day from First Administration
- SAE (Yes/No).

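### No planned summary gives the number of patients who ever reached Grade 3 or 4 lymphopenia, although the protocol makes it an adverse event of special interest

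*SAP*

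**What the plan says.** Protocol 11.1 lists among the AESIs "Severe lymphopenia: defined as Grade 3 (<500 to 200 cells per microliter) or Grade 4 (<200 cells per microliter". The definition rests on the absolute lymphocyte count (ALC) alone and does not require symptoms. The same section says that AESIs are collected through the SAE procedure, and protocol 11.5 requires them to be reported even when non-serious.

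SAP 5 carries over the objective of collecting "adverse events of special interest (AESIs) and special situations during treatment with cladribine tablets over a 24-month period", names AESIs as an endpoint and refers the analysis to Section 15.

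SAP 15.3 plans this for ALC: "An additional summary of ALC by lymphopenia grade will be presented with proportion of patients in each category at each time point". Its limits for Grades 3 and 4 match the protocol's: 0.2 to <0.5 x 10^9/L is 200 to <500 cells per microliter.

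On extra sampling, protocol 9.1.1 says: "If the ALC drops to <500 cells per microliter, the patient should be actively monitored until values increase as per USPI". It asks that the additional unscheduled assessments be documented. The only general SAP rule that applies is in Section 9 (Time window), which analyses endpoints without a window by the visit recorded in the eCRF, where available.

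**The concern.** For an event defined by a laboratory threshold and described as transient, the basic safety figure is the number of patients who crossed the threshold at any time. A set of visit proportions is a different quantity. One patient may be low at several visits, and another may be low only between visits, so the rows neither add up to the patient count nor reveal it.

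Extra sampling starts below 500 cells per microliter, which is the Grade 3 limit. The deepest values may therefore come from unscheduled samples, and the SAP does not say whether these enter any summary.

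What is at stake is a named safety endpoint in a study whose main research question includes safety. If the count is added only when the report is written, SAP 4 requires it to be identified as post hoc or unplanned.

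**Working it through.** The plan states no figure on this point, so there is none to reproduce. The check has three parts.

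**1. What each output in SAP Section 15 delivers**
- 15.1.1, overall table: no AESI row. It includes "Any TEAE by severity (Severe, Moderate, Mild"), but that scale is functional. Protocol 11.2 defines severe as "Significant impairment of functioning: the patient is unable to carry out usual activities", which is not a cell-count grade.
- 15.1.1, table by system organ class and preferred term: counts reported lymphopenia terms, without grade.
- 15.1.1, listing: no grade and no AESI column.
- 15.1.2: only events leading to interruption, permanent discontinuation or dose reduction.
- 15.2: deaths and SAEs only.
- 15.3: ALC grade by time point, boxplots, a median line graph, and a listing with values, dates and a Low/High flag.

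None of these is a per-patient Grade 3 or 4 figure.

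**2. What the visit rows can tell**

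Protocol Table 1 marks K = 6 post-baseline hematology visits (Months 2, 6, 12, 14, 18, 24). Let p_k be the proportion at Grade >=3 at visit k, and P the proportion at Grade >=3 at one or more of these visits. With the same denominator at every visit:

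max(p_k) <= P <= min(1, sum of p_k)

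- Assumed rows of 5% at all six visits: 5% <= P <= 6 x 5% = 30%.
- In reverse, for P = 20% to 25%, the largest row could be as low as 20/6 = 3.3% to 25/6 = 4.2% (each affected patient low at one visit, evenly spread). It could be as high as 20% to 25% (all low at the same visit).

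SAP 9 bases visit percentages on patients still in the study, so under dropout these bounds hold only approximately.

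**3. Illustration on assumed inputs**

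The documents give no episode timing, so all of the following is assumed:
- The true proportion ever affected is E = 20% or 25%, a range borrowed from protocol 7.4 as an input only.
- Each affected patient has one episode, half of them after each course, and the second course starts at Month 12.
- Onset is uniform from 1 to 6 months after course start, and the episode lasts d months, with d from 1 to 4.
- There is no dropout, and samples are taken at scheduled visits only.

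Within a course, the 2-month visit catches onsets in months 1 to 2, a share of 1/5. The 6-month visit catches onsets in the last d months of the window, a share of d/5. The 12-month visit catches none. For d <= 4 the two sets do not overlap.

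- Peak visit row = 0.5 x (d/5) x E
- Worst-grade table = ((1 + d)/5) x E

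| Episode length | Peak visit row | Worst-grade table | Truly ever affected |
|---|---|---|---|
| d = 1 month | 0.5 x 1/5 x E = 2.0-2.5% | 2/5 x E = 8-10% | 20-25% |
| d = 4 months | 0.5 x 4/5 x E = 8-10% | 5/5 x E = 20-25% | 20-25% |

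The part due to table layout is the gap between the second and third columns. For 1-month episodes, the remaining gap to the fourth column is a limit of sampling, and changing the table does not close it.

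**The case against.** Several arguments on the other side have force.

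- **Severe lymphopenia is counted somewhere.** A reader might infer that Section 15 leaves it out altogether. It does not: reported terms appear in the preferred-term table. What is missing is the grade, so milder reported cases cannot be separated from Grade 3 or 4.
- **Capture is required.** Protocol 11.5 says abnormal laboratory findings "should not be reported as AEs unless they are associated with clinical signs and symptoms or are considered otherwise medically important by the investigator". A reader might infer that most Grade 3 or 4 values never reach the safety data. The specific AESI duty in protocol 11.1 and 11.5 points the other way, so the gap is mainly one of tabulation.
- **Unscheduled values are not lost.** They are to be documented, and the SAP 15.3 listing carries visit, date and value, so a hand count is possible. The SAP is silent on tabulating them, and output shells that are not in these documents may settle it. A listing is still not a planned summary.
- **The 20-25% is background.** Protocol 7.4 reports that "Approximately 20% to 25% of the patients treated with 3.5 mg/kg as monotherapy developed transient Grade" 3 or higher lymphopenia in earlier trials. A reader might infer a planned comparison that the visit rows would distort. No objective or analysis compares this cohort with those trials.
- **The size is assumed.** The range for the largest row, 3.3% to 25%, includes no discrepancy at all. Setting a 2.0-2.5% row against 20-25% would overstate what the layout causes.
- **Some SAP sections are blacked out.** A further lymphocyte analysis there cannot be excluded. SAP 5 nevertheless sends AESIs to Section 15, where no redaction is visible.
- **The study is descriptive and single-arm, and every value is kept.** This limits the harm and makes the point one of reporting.

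**Conclusion.** The point holds as a reporting gap. Followed exactly, the visible plan gives no count of patients who ever reached ALC Grade 3 or 4, although the protocol defines that event and the SAP names its class as an endpoint. It gives only visit-by-visit grades and an ungraded count of reported terms, and does not say whether unscheduled samples enter any summary.

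With a constant denominator, no visit row can exceed the proportion ever affected, so reading a row as that proportion can only understate it. By how much cannot be determined from the documents. On the assumed inputs, the peak row is about a quarter of what a worst-grade table would show for 1-month episodes (2.0/8) and two fifths for 4-month episodes (8/20).

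The documents do not support saying that severe lymphopenia goes unreported, that the data are lost, or that a new table would always recover the true proportion. The change is worth making because it is cheap and delivers a named safety endpoint. The primary endpoint is unaffected.

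**What to change.** In SAP 15.3, add one table of each patient's worst ALC grade after first dose and up to the end of follow-up. Use the SAF and all scheduled and unscheduled samples. Give n/N for Grade 3, Grade 4 and Grade >=3, with the Clopper-Pearson interval already set in SAP 9.

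State that unscheduled ALC values enter this table and the listing, but not the by-visit rows.

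In SAP 15.1.1, add a row for each AESI in protocol 11.1.

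The cost is SAP wording, one derived variable and a few table rows. The values, dates and grade limits are already specified, and no new data are needed. The downside is that patients sampled more often have more chances to show a low value, so report the number of ALC samples per patient beside the table.

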#### 15.4 Vital Signs

Weight will be collected at Baseline when available. It will be summarized descriptively.

Unit Conversion:

Weight (Kg) =  $0.4536^*$  Weight (lb)

## 15.5 Other Safety or Tolerability Evaluations

Physical examination as per standard of care will be performed at Baseline. The number and percentage of patients completing the physical examination will be reported.

Neurological examination as per standard of care will be performed at Baseline and at Visit 2, 3, 5 and 6. During the examination, if Kurtzke Functional System Scores , ambulation up to 500 meters and Expanded Disability Status Score are collected as standard of care, they will be reported and evaluated. No imputation will be performed if any items in the above examinations are missing. Visit values (including Baseline) and change from baseline values will be considered. All the items will be summarized descriptively.

## 16 Analyses of Other Endpoints

## 16.3 Patient-Reported Outcome

Analysis (Analysis Population)	Derivation	Statistical Analysis Methods	Missing data handling
Secondary Er	ndpoints: ePROs		
Secondary (FAS)	Scores collected at Baseline and at Month 6, 12 and 24 for the following PROs (TSQM, SF-36, MFIS-5, BDI-FS, WPAI-MS)	Baseline scores and change from baseline scores will be summarized descriptively	See description in section 16.3
	Scores collected at Baseline and at Month 6, 12, and 24 for PDDS	Baseline scores and change from baseline scores will be summarized descriptively	See description in section 16.3

BDI-FS: Beck-Depression Inventory-Fast Screen; FAS: Full Analysis Set; MFIS-5: Modified Fatigue Impact Scale – 5-Item Version; MS: Multiple Sclerosis; PDDS: Patient Determined Disease Steps; SF-36: 36-Item Short Form Health Survey; TSQM: Treatment Satisfaction Questionnaire for Medication, WPAI-MS: Work Productivity Activity Impairment.

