8.2 Secondary Objectives

- To assess PROs, treatment adherence and treatment satisfaction during treatment with cladribine tablets
- To assess treatment patterns (MS treatment prior to transition to cladribine tablets, since MS diagnosis, concomitant treatment for MS during the last 2 years prior to initiation of cladribine tablets (or since MS diagnosis, if diagnosis <24 months), follow-up treatment in case of discontinuation of cladribine tablets)
- To estimate the ARR over the 24-month period prior to initiation of cladribine tablets (or since MS diagnosis, if diagnosis <24 months)

• To collect all serious adverse events (SAEs), adverse drug reactions (ADRs), adverse events of special interest (AESIs) and special situations during treatment with cladribine tablets over a 24-month period

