9.2.3 Observation Period

Each patient will be followed from the date of first dose of cladribine tablets until loss to follow-up, withdrawal of consent, death or the end of the data collection period, whichever comes first. Patients will be followed for 24 months from first dose and up to 30 months for those patients who may require a delay of initiation of Year 2 treatment for up to 6 months due to low lymphocyte counts. Follow-up will continue regardless of cladribine tablets discontinuation.

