- Medication log containing other MS DMD treatments (if applicable) during the study period, including medication doses and routes of administration, start dates, stop dates and reasons for discontinuation
- Relapse of MS during the study period as determined by the investigator (see Section 9.1.2.1 for a guide on definition) including date of onset, resolution of relapse and definition for relapse used
- Relapse of MS associated with hospitalization (relapse as primary diagnosis or reason for hospitalization) during the study period as determined by the investigator (see Section 9.1.2.1 for a guide on definition) including date of onset, resolution of relapse and definition for relapse used
- Relapse of MS associated with glucocorticoid use during the study period as determined by the investigator (see Section 9.1.2.1 for a guide on definition) including date of onset, resolution of relapse and definition for relapse used
- MRI scans from all MRIs performed during the study period; MRI scans are assessed by a central neuroradiology center; data includes:
- Results of neurological examination as per standard of care (Kurtzke FSS, ambulation up to 5000 meters and EDSS)
- Hematology assessment (white blood cell count, hemoglobin, hematocrit, platelet count, ALC). If the investigator assesses JCV status, these data should be recorded as well
- Pregnancy, HIV, hepatitis B, hepatitis C and tuberculosis test results
- Comorbid conditions

- AEs as a continuous log
- ePRO assessments (treatment adherence questions based on modified versions of the MS-TAQ, TSQM, SF-36, MFIS-5, BDI-FS, WPAI-MS, PDDS)

[figure not shown]
Derived and transformed data needed for the analysis are described in Section 9.7.2.

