## 8.2 Definition of Analysis Populations and Subgroups

#### Full Analysis Set (FAS)

The FAS includes all patients enrolled in the study who received at least 1 dose of cladribine tablets.

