The number and percentage of patients who started another MS treatment after discontinuation of cladribine tablets will be reported (using the number of patients who discontinue cladribine tablets as denominator).

Reasons for discontinuation of cladribine tablets will be collected and for each reason, the corresponding number and percentage of patients will be reported (using the number of patients who discontinue cladribine tablets as denominator).

A listing of concomitant MS medications started after discontinuation of cladribine tablets will be provided. The following variables will be reported:

- Patient ID
- Medication name
- Visit
- Dose
- Unit
- Frequency
- Route of administration
- Start Date / Ongoing (Yes/No) / Stop Date
- Last study treatment administration date

The elapsed time to discontinuation of cladribine tablets will be calculated as:

*elapsed time to discontinuation of cladribine tablets = Date of discontinuation of cladribine tablets – Date of first study dose* 

It will be summarized as a continuous variable and also reported through a KM analysis. The 'Last study treatment administration date' according to the Treatment Termination form will be used as date of discontinuation of cladribine tablets (both for patients early discontinuing the treatment and for patients completing the treatment; for patients completing the treatment this will be a censoring date).

Number of doses and % of planned doses (as per USPI) received will be summarized descriptively.

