## 18 Appendices

#### **TSQM** items

1. How satisfied or dissatisfied are you with the ability of the medication to prevent or treat your condition? (Score 1 to 7)

2. How satisfied or dissatisfied are you with the way the medication relieves your symptoms? (Score 1 to 7)

3. How satisfied or dissatisfied are you with the amount of time it takes the medication to start working? (Score 1 to 7)

4. As a result of taking this medication, do you currently experience any side effects at all? (Score 0[No] or 1[Yes])

5. How bothersome are the side effects of the medication you take to treat your condition?

(Score 1 to 5)

6. To what extent do the side effects interfere with your physical health and ability to function (i.e., strength, energy level, etc.)?

(Score 1 to 5)

7. To what extent do the side effects interfere with your mental function (i.e., ability to think clearly, stay awake, etc.)?

(Score 1 to 5)

8. To what degree have medication side effects affected your overall satisfaction with the medication? (Score 1 to 5)

9. How easy of difficult is it to use the medication in its current form?

(Score 1 to 7)

10. How easy or difficult is it to plan when you will use the medication each time?

(Score 1 to 7)

11. How convenient or inconvenient is it to take the medication as instructed?

(Score 1 to 7)

12. Overall, how confident are you that taking this medication is a good thing for you? (Score 1 to 5)

13. How certain are you that the good things about your medication outweigh the bad things? (Score 1 to 5)

14. Taking all things into account, how satisfied or dissatisfied are you with this medication? (Score 1 to 7)

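### The TSQM summaries have no rule for scores given after a switch to another DMD, so the cladribine satisfaction result can include ratings of another medicine

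*SAP*

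**What the plan says.** The secondary objective in Protocol 8.2 is "To assess PROs, treatment adherence and treatment satisfaction during treatment with cladribine tablets". SAP section 5 repeats it and lists the TSQM among the endpoints.

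SAP 16.3 names the FAS as the population for "Scores collected at Baseline and at Month 6, 12 and 24 for the following PROs", and the list that follows begins with the TSQM. SAP 8.2 defines the population: "The FAS includes all patients enrolled in the study who received at least 1 dose of cladribine tablets". Being still on cladribine, or free of another DMD, is not a condition.

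Protocol 9.2.3 states: "Follow-up will continue regardless of cladribine tablets discontinuation". Protocol 9.3 provides for a "Medication log containing other MS DMD treatments (if applicable) during the study period", with start and stop dates. SAP 13 adds: "The number and percentage of patients who started another MS treatment after discontinuation of cladribine tablets will be reported".

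The TSQM items in SAP 18 refer to the medication without naming it. The last item, for example, reads: "Taking all things into account, how satisfied or dissatisfied are you with this medication".

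**The concern.** The TSQM differs in kind from the other PROs. SF-36, MFIS-5, BDI-FS, WPAI-MS and PDDS measure the patient's state, and that quantity stays the same whatever drug is being taken. The TSQM rates a drug. Once a patient takes a different DMD, the thing being rated may have changed while the score still enters the same column.

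At stake is the meaning of the TSQM means and changes from baseline, chiefly at Months 12 and 24, because switches accumulate over time. A reader would take these figures as satisfaction with cladribine. With the planned outputs, that reader could not tell how many of the scores were given after another DMD was started, or what the mean would be without them.

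**Working it through.** The documents give no expected TSQM score, switch rate or precision target, so there is no planned figure to reproduce. The check has two parts.

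**1. Does any visible rule separate post-switch scores?**

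- SAP 8.2, analysis table: PROs are marked for the FAS and the Safety Analysis Set (defined identically), and not for the Per Protocol set.
- SAP 8.2, subgroups: treatment non-completers are defined as a subgroup, but subgroup analyses are planned for the primary endpoint only.
- SAP 9, time window: the TSQM counts within ±30 days of Months 6, 12 and 24 from Day 1. Treatment status plays no part.
- SAP 16.3, TSQM scoring: a domain score depends only on how many items are missing.
- SAP 13: switching is counted with patients who discontinue cladribine as the denominator, and later MS medications are listed with dates. Neither output is tied to TSQM responders at a given time point.

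None of these excludes, flags or separates a TSQM score given after another DMD is started.

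The item wording leaves the reference drug open. The adherence questionnaires in SAP 18 do not: one version is for the previous self-injectable and the other names cladribine tablets. Scoring shows how the mixing would work. TSQM item 4 asks about current side effects, and a No gives 100 on the Side Effects domain. A patient with no side effects on a new DMD who answers about that drug would contribute 100 to the cladribine summary.

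**2. How far could the mean move?**

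Let f be the share of TSQM responders at a time point who rate another drug, and Δ the mean score for that drug minus the mean score for cladribine, on the 0–100 scale.

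All-FAS mean = (1 − f) × cladribine mean + f × (cladribine mean + Δ) = cladribine mean + f × Δ

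The shift is therefore f × Δ. Both inputs are assumptions:

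| f | Δ = ±10 points | Δ = ±20 points |
|---|---|---|
| 2% | ±0.2 | ±0.4 |
| 5% | ±0.5 | ±1.0 |
| 10% | ±1.0 | ±2.0 |
| 20% | ±2.0 | ±4.0 |
| 30% | ±3.0 | ±6.0 |

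The sign depends on whether the later drug is rated better or worse, which the documents do not indicate.

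**The case against.** The strongest defence is that the all-FAS summary is deliberate. Cladribine is given in short courses, and the protocol applies the idea of being under cladribine treatment to the whole 24 months, both for the primary outcome (Protocol 9.1.2.1) and for the safety objective (8.2). SAP section 5 sets the PRO time frame as 24 months from enrolment. On that reading the planned summary matches the endpoint definition. This stands as a reason to keep the all-FAS summary. It does not settle which drug a post-switch score describes.

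Second, the appendix shows only the TSQM items. Any lead-in text on the electronic form is not shown and might name the drug to be rated. This also stands. A reader might infer that the reported satisfaction definitely does include ratings of other medicines. The documents support only that it can: at least one patient must switch, complete an in-window TSQM and answer about the new drug. The same limit applies at baseline. SAP 9 says baseline PROs precede the first cladribine dose, but does not say which drug the baseline TSQM rates.

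Third, a reader might infer that the mixed-in scores come from patients for whom cladribine failed. The documents do not support this. Protocol 11.4 lists pregnancy, infection and renal impairment among the reasons to stop, and 9.2.2 adds slow lymphocyte recovery.

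Fourth, SAP 13 already reports switching. This helps a reader judge its overall extent but does not separate the TSQM scores.

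Finally, SAP section 12 and parts of sections 14 and 16 are blacked out. The TSQM text in 16.3 is visible and contains no such rule.

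**Conclusion.** The point holds as a gap in the analysis plan. TSQM summaries on all FAS patients with an in-window assessment can include ratings of another medicine, mainly at Months 12 and 24, and the planned outputs give no way to separate them.

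The size is unknown. Under the assumptions tabulated it runs from 0.2 points (2% switched, 10-point difference) to 6 points (30%, 20-point difference), in either direction. A reader might infer that the Month 12 and 24 means cannot be read as satisfaction with cladribine at all. That goes too far: with few switches the effect is small, and no switch rate is given.

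The endpoint is secondary and descriptive, with no test or decision threshold attached. This is a cheap improvement that makes the result answer its stated objective. It does not threaten the study's main conclusion.

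**What to change.** In SAP 16.3:

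- State which drug the TSQM refers to at each time point, including any lead-in text on the electronic form.
- Report TSQM assessments made before the first dose of another DMD as the cladribine satisfaction result, using the logged DMD start dates.
- Show TSQM assessments made after that date separately, with the number of patients before and after a switch at each time point.
- Keep the all-FAS summary as supportive.
- Leave SF-36, MFIS-5, BDI-FS, WPAI-MS and PDDS on all follow-up.

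The cost is a short addition to the SAP and one date filter on data already collected. No new data collection is needed.

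There are two downsides. The pre-switch summary has fewer records, most noticeably at Month 24. It also describes patients who had not switched, a group that may be selected for satisfaction, so it must be read beside the switch counts and the all-FAS summary. Patients who stop cladribine and start nothing else stay in the pre-switch summary; the filter does not address them.
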